4.1. Test Product

Below is the description of the test product and its ingredients.

Upset Stomach Relief Product

Description: Combining Deglycyrrhizinated licorice (DGL), Artichoke Leaf, Marshmallow Root, Ginger, and Chamomile for comprehensive, yet gentle plant-based support for occasional indigestion and heartburn relief. This formula is designed to promote digestion and feelings of digestive comfort.

Active Ingredients: Licorice Extract, Artichoke Leaf Extract, Chamomile, Marshmallow Root, Ginger.

Inactive Ingredients: Capsule (Hydroxypropyl Methyl Cellulose, Purified Water, Carrageenan, Potassium Chloride), Rice Hull Concentrate.

4.2. Required Behavior

During the hour directly following consumption of the test product, no medication or supplementation (including all CBD products) other than the test product should be taken

for relief of indigestion and heartburn symptoms. Once the 1-hour report has been recorded the participant may take other medications or supplements. If medication is taken, the participant will record this in their symptom diary.

Participants are asked to limit the consumption of alcohol beverages to less than or equal to two drinks per day.

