- A longitudinal analysis will be performed for participants who report on more than one incident of heartburn or indigestion.
- Adverse events will be summarized.
- An additional data presentation will consist of results from both Treatment and Control
 in similar studies appearing in the literature. There will be no formal statistical
 comparison of results from this study and historical studies.
- The Net Promoter Score will be summarized and compared against outcomes.
- Comparison against normal behavior will use the paired sample t-test.

4. Study Design

The present study will be a single site, prospective, one arm observational study of minimal risk consisting of at least 200 participants who suffer from symptoms of occasional indigestion and heartburn. The participants must meet additional inclusion/exclusion criteria (see Inclusion/Exclusion Criteria). Participants will begin taking the capsules at the onset of indigestion and heartburn symptoms. Onset is defined as the point in time the participant takes the test product for relief of symptoms. When the participant decides to take the test product, they will report and rate their symptoms on a 4-point Likert scale in the symptom diary prior to taking the test product. After consuming the test product, the participant will complete a 4-point Likert scale for each symptom at 15 minutes, 30 minutes, and 1 hour after taking the test product. If needed the participant will be allowed to take an alternative medication an hour after taking the test product. If medication is taken, the participant will record this in their symptom diary.

Study enrollment and management will be decentralized, where participants do not visit an investigator or a clinic for clinical assessment. The participants will participate in the study at home. All data collected from during this study will be reported by the participant via eCRFs, eDiary, and other electronic data entries. If a visit is required, it will be conducted via remote contact by telephone.

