6.1. Study Procedures

- Candidates will review information about the study and complete a screening form.
- During the screening process, the candidate will be asked questions regarding their symptoms and medical history to ensure that they meet the requirements to participate in this study.
 Potential participants will also be asked questions to ensure that they do not meet any of the exclusion criteria and meet all of the inclusion criteria.
- After successful screening (participant does not meet any exclusion criteria), participants will review and sign study informed consent form.
- Upon verification of signed informed consent, participant will be enrolled into the study.
- At time of enrollment, participant will be given access to the HIPAA compliant study portal.
 - The study portal provides access to study information, signed informed consent form, instructions for test product use, frequently asked questions, study surveys, symptom diary, and data collection tools.
- Participant shall complete baseline assessments upon access to the portal.
 - Baseline assessment will include questions regarding the participants' demographics, medications, detailed information regarding their indigestion/heartburn including treatment.
- To ensure that baseline assessments are completed before test product is used by the
 participant, study materials and study welcome package will be shipped to the participant once
 the clinical study manager/clinical ops coordinator confirms that the baseline assessment has
 been completed.
- The welcome package will include an information sheet that will outline instructions for their participation in the trial, the test product, and paper forms of the documents (paper form of

- study documents will be provided for real time data collection, in the event that the participant cannot log into the study portal to input data).
- Once the participant receives the test product, the participant will log into the study portal to acknowledge the receipt of the test product.
- Study start date will be the reported date of receipt of test product.
- Participant will be sent weekly email reminders that remind them of their participation in the study.
- At the onset of the indigestion and heartburn episode, the participant will start a Symptom Diary and complete a 4-point Likert scale for each of the symptoms they are experiencing.
 - Onset is defined as the point in time the participant takes the test product for relief of symptoms.

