- After completing the surveys, the participant will take the test product. The participant will take
 2 capsules per indigestion and heartburn episode. With a max of 6 capsules per day. (If
 participant takes 6 capsules in 1 day this will be defined as 3 indigestion and heartburn episodes
 and the participant will be exited from the study).
- After taking the test product, the participant will complete a 4-point Likert scale assessment for each symptom at 15 minutes, 30 minutes, and 1 hour after taking the test product.
- When the participants symptoms have resolved , the participant will complete the symptom diary.
- If the participant takes any other medication outside of the test product, the participant will record this on the symptom diary.
 - The participant is allowed to take alternative medications or supplements AFTER 1 hour from taking the test product.
- After taking the test product, the participant will be instructed to fill out an Adverse Event form for any side-effects experienced.
- After the first episode of indigestion and heartburn, the participant will be asked to complete the same process for another 2 episodes within the 60-day study time frame; however, these are not required.
- If the participant completes the required assessments for a total of 3 episodes of indigestion and heartburn, they will be prompted, by email, to exit the study.
- If the participant only completes the required assessments for the required 1 episode of indigestion and heartburn, the participant will be prompted, by email, to complete the study exit form and will be exited from the study on day 60 (60 days from the day of receipt of the test product).
- Neither the sponsor nor Hawthorne Effect Inc. will not collect any unused test product.
- Upon receipt of study exit survey and review of completed study forms, participant will receive an Amazon gift card of \$25 via email.

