13.1.5. Appendix E Symptom Diary

Please complete the following items during your first episode of Indigestion/Heartburn. We encourage you to complete the forms online in real time. However, if you cannot log into your patient portal at the time of your symptoms please complete these forms and log into your patient portal as soon as possible and complete the online forms.

Reminder: Do not take any other medications or supplements within the first hour of taking the test product.

Date of Onset:	Ti	me of Onset:	
Trigger (check all that apply Food □ Caffeine □ Alcol □ Smoking □Other:	nol		
Time test product taken:			
Please rate the followin answer.	g symptoms at th	e following time point	s. Circle one
Onset (Prior to Bloating 0 No Symptom		2	3
No Symptom	Slight	Moderate	Severe

Early Fullness During a 1	Meal	2	3			
No Symptom	Slight	Moderate	Severe			
Pain or Discomfort in the	e Upper Abdomen	2	3			
No Symptom	Slight	Moderate	Severe			
Burning in the Upper Ab		2	2			
0 No Symptom	1 Slight	2 Moderate	3 Severe			
Pain/Burning in the center	er of your chest					
0 No Symptom	l Slight	2 Moderate	3 Severe			
J 1	S					
Nausea						
0 No Symptom	1 Slight	2 Moderate	3 Severe			
1 to Symptom	Siigiit	Woderate	Severe			
Vomiting						
0 No Symmton		2 Madamata	3			
No Symptom	Slight	Moderate	Severe			
Burping						
0	1	2	3			
No Symptom	Slight	Moderate	Severe			
Other						
0	1	2	3			
No Symptom	Slight	Moderate	Severe			
15 Minutes after taking the test product						
Bloating						
0	1 Slight	2 Moderate	3 Sayara			
No Symptom	Slight	Moderate	Severe			

Early Fullness During a Meal 0 1 2 3							
No Symptom	Slight						
Pain or Discomfort in the	Upper Abdomen	_	_				
0	I C1: 14	2	3				
No Symptom	Slight	Moderate	Severe				
Burning in the Upper Abo	lomen						
0	1	2	3				
No Symptom	Slight	Moderate	Severe				
Pain/Rurning in the center	r of vour chost						
Pain/Burning in the cente	1	2	3				
No Symptom	Slight	Moderate	Severe				
- · · · · · · · · · · · · · · · · · · ·	38		20100				
Nausea							
0	1	2	3				
No Symptom	Slight	Moderate	Severe				
Vomiting		_	•				
0	l C1: 14	2	3				
No Symptom	Slight	Moderate	Severe				
Burping							
0	1	2	3				
No Symptom	Slight	Moderate	Severe				
Other:							
0	1	2	3				
No Symptom	Slight	Moderate	Severe				
30 Minutes after taking the test product							
Bloating							
0	1	2	3				
No Symptom	Slight	Moderate	Severe				

Early Fullness During a M	Meal		3		
0 No Symptom	2				

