Dain or Discomfort in the	Unner Abdemen				
Pain or Discomfort in the	Opper Abdomen	2	3		
No Symptom	Slight	Moderate	Severe		
Burning in the Upper Ab	domen				
0 No Symptom	1 Slight	2 Moderate	3 Severe		
Pain/Burning in the center	er of your chest				
0	1	2	3		
No Symptom	Slight	Moderate	Severe		
Nausea					
0	1	2	3		
No Symptom	Slight	Moderate	Severe		
Vomiting					
0	1	2	3		
No Symptom	Slight	Moderate	Severe		
Burping					
0	1	2	3		
No Symptom	Slight	Moderate	Severe		
Other:	1	2	3		
0 No Symptom	Slight	Moderate			
No Symptom	Stight	Woderate	Severe		
60 Minutes afte	er taking the	e test product			
Bloating					
0	1	2	3		
No Symptom	Slight	Moderate	Severe		

Early Fullness During a Meal 0 No Symptom	1 Slight	2 Moderate	3 Severe		
Pain or Discomfort in the Upp 0 No Symptom	oer Abdomen 1 Slight	2 Moderate	3 Severe		
Burning in the Upper Abdom 0 No Symptom	en 1 Slight	2 Moderate	3 Severe		
Pain/Burning in the center of 0 No Symptom	your chest 1 Slight	2 Moderate	3 Severe		
Nausea 0 No Symptom	1 Slight	2 Moderate	3 Severe		
Vomiting 0 No Symptom	1 Slight	2 Moderate	3 Severe		
Burping 0 No Symptom	1 Slight	2 Moderate	3 Severe		
Other: 0 No Symptom	1 Slight	2 Moderate	3 Severe		
After your symptoms resolveplease complete any of the following questions if applicable.					
Did your symptoms resolve completely with the test product? Yes No Time of complete symptom resolution:					

Did you need to take another medication	on: Yes N	No
Medication #1:	Dose:	Time:
Medication #2:	Dose:	Time:
Medication #3:	Dose:	Time:
Did your symptoms resolve completely	with taking your altern	native medication? Yes No
After taking the alternative medication,	, time of complete resol	lution of symptoms:

Did you experience any side effects after taking the test product? (Y/N) If yes, **Please fill out** the Adverse Event form.

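### Section 4.2 makes the 1-hour report a condition for taking another remedy, but sections 4 and 6.1 and the diary reminder require only an elapsed hour, so a late 60-minute rating can follow a permitted remedy.

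*Combined protocol and SAP*

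**What the plan says.** The protocol says in four places when a participant may turn to another remedy.

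- Section 4.2 bars other remedies during the hour after the dose and then ties release to the rating: "Once the 1-hour report has been recorded the participant may take other medications or supplements".
- Section 4: "If needed the participant will be allowed to take an alternative medication an hour after taking the test product".
- Section 6.1: "The participant is allowed to take alternative medications or supplements AFTER 1 hour from taking the test product".
- Appendix E, on the form where the ratings are made: "Do not take any other medications or supplements within the first hour of taking the test product".

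The last three do not mention the rating. Appendix B, the instructions for use, is silent on other remedies.

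The diary has a field for "Time test product taken". Under "Did you need to take another medication" it gives dose and time lines for up to three medications. Those lines come after the instruction "After your symptoms resolveplease complete any of the following questions if applicable", so they are completed later. The 60-minute block has only its nominal heading, with no actual time of completion.

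Section 7.1 makes 60 minutes one of three post-dose primary time points, each compared with the pre-dose rating, with no control group. Section 7.3 gives no rule for a rating made after another remedy, but leaves detail to an SAP still to be written.

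**The concern.** The condition that protects the 60-minute rating is missing from the form that participants have in front of them. Someone who is late with that rating can obey the diary, take an antacid just after the hour and then rate. They would breach section 4.2 without knowing it.

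A person who wants another remedy at one hour is probably still symptomatic. If the remedy works, the recorded improvement is credited to the test product. The primary analysis is a within-person change with no concurrent control, so nothing in the design offsets this. The stake is a modest upward lean in one of three primary time points.

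**Working it through.** **1. The plan's own figure.** Section 7.2 assumes a mean improvement of 0.5 and an SD of 1.5, and gives 97 participants for 90% power with the paired t-test. The significance level is not stated. With two-sided 5% (an assumption) and a standardised effect of 0.5/1.5 = 0.333, noncentral-t power is 0.8985 at n = 96 and 0.9015 at n = 97. So 97 is reproduced; one-sided 5% would give 79. The sample size is not in question. The standard error that follows is 1.5/√97 = 0.152.

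**2. Who is exposed.** A rating made on schedule at 60 minutes precedes any permitted remedy under all four wordings. Exposure needs both a late 60-minute rating and a remedy taken between the hour and that rating.

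**3. Size of the bias.** The documents give none of these inputs, so all are assumptions:

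- f, share of episodes with another remedy soon after 60 minutes: 10% to 20%
- q, share of those episodes rated after the remedy: 10% to 50%
- d, extra drop in the rating due to the remedy: 0.25 to 0.5 point

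Bias in the mean 60-minute change = f × q × d. The share of all 60-minute ratings affected is f × q, from 1% to 10%, or about 1 to 10 of 97. The last column is the rejection rate of the two-sided 5% test when there is no true effect (noncentral t, 96 df).

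| f | q | d | Bias (points) | Bias / 0.5 | Bias / SE | Rejection |
|---|---|---|---|---|---|---|
| 0.10 | 0.10 | 0.25 | 0.0025 | 0.5% | 0.02 | 5.0% |
| 0.20 | 0.25 | 0.5 | 0.025 | 5% | 0.16 | 5.3% |
| 0.20 | 0.50 | 0.5 | 0.05 | 10% | 0.33 | 6.2% |

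The bias is proportional to each input. If d were 1 point in the last row, the bias would be 0.20 × 0.50 × 1 = 0.10.

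**4. What it would take to matter.** Half a standard error is 0.0762 points. At d = 0.5 that needs 0.0762/0.5 = 15.2% of ratings affected, about 15 of 97. At d = 0.25 it needs 30.5%, about 30 of 97.

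**5. Can the existing data deal with it?** Dose and remedy times identify the episodes with a remedy soon after 60 minutes. Suppose the 30-minute rating replaces the 60-minute rating in all of them. If those participants would truly have improved by u between 30 and 60 minutes, the error is −f × u. With u = 0 it is 0. With u = 0.25 and f = 0.20 it is −0.05, so the result is conservative. If they worsened over that half hour, the sign reverses. Knowing the actual time of the rating would limit the substitution to the share f × q. With q = 0.25 that is 0.05, and the error at u = 0.25 shrinks to −0.05 × 0.25 = −0.0125.

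**The case against.** The best reply is that the four statements hardly conflict. The rating is due at one hour and the remedy is allowed only after it. Sections 4 and 6.1 mention the 1-hour rating before the remedy allowance. Section 4.2 states the order outright, and the other places are shorter rather than contrary. The plan also works against lateness: the diary encourages real-time completion, and section 6.1 says paper "study documents will be provided for real time data collection" when the portal cannot be reached. Section 11 already discloses reliance on self-report. All of this stands, and it is why the point is minor. It does not remove the gap for late raters, who are the people section 4.2 would protect.

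A second reply is that some material is not in the reviewed text. The product insert, information sheet and FAQs may carry the 4.2 condition, and the SAP may supply a handling rule. That also stands. It argues for checking those items, not for leaving the diary reminder as it is.

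A reader might infer that, because the diary does not show whether rating or remedy came first, every episode with a remedy soon after 60 minutes would have to be excluded, at the price of a larger selection bias. The documents do not support this. Section 7.2 says the analysis uses the data as they are collected, and no exclusion is proposed. As step 5 shows, the 30-minute rating can be substituted using times the diary already records.

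**Conclusion.** The inconsistency is real and minor. It affects only late 60-minute ratings that follow another remedy. Any bias is probably upward, on the reasoning that people who take another remedy at one hour are still symptomatic. Within the assumed ranges it is 0.0025 to 0.05 points, at most 10% of the planned improvement and about 0.33 standard errors. The documents supply neither the rate of late rating nor the effect of a remedy, so its actual size is unknown.

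A reader might go further and doubt the 60-minute result or the primary conclusion. The documents give no ground for that: on-time ratings are safe, the 15- and 30-minute results are reported separately, and a bias of half a standard error would need roughly 15 to 30 of 97 ratings affected at the assumed drops.

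The change is still worth making. The rule is already the sponsor's own, and the diary is where participants will see it.

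**What to change.** 1. In sections 4 and 6.1, add that the 60-minute ratings must have been recorded before another remedy is taken, as section 4.2 already requires.
2. Change the end of the Appendix E reminder so that the ban runs *until one hour has passed and you have recorded your 60-minute ratings*. Check that the insert, information sheet and FAQs agree.
3. In section 7.3 or the SAP, add: *As a sensitivity analysis, the 60-minute result will also be reported with the same episode's 30-minute rating substituted wherever another remedy was taken soon after 60 minutes, as identified from the recorded dose and remedy times.* Fix the window for 'soon after' before the data are seen, and allow for remedy times entered from recall. The substitution assumes that the one-hour ban was kept and the 30-minute rating was made on time. It is conservative if these participants improved between 30 and 60 minutes.
4. Optional: a field for the actual time of the 60-minute rating. It would confine the substitution to ratings truly made after a remedy, but the sensitivity analysis does not depend on it.

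The primary analysis and sample size do not change. The cost is slightly longer wording in three places, one analysis sentence, and a 60-minute sensitivity result that may be slightly less favourable.

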2.2.2. Known Potential Benefits

Over-the-counter and prescription remedies for occasional indigestion and heartburn have known undesirable side effects. Additionally, these products often contain additives, dyes, fillers and other unnatural or synthetic ingredients that consumers are looking to avoid. As such, these consumers are seeking natural, plant-based alternatives for symptom relief. Research participants may benefit from the intervention by eliminating such unwanted side effects when treating their symptoms of occasional indigestion and heartburn while achieving symptom relief. If the intervention is shown to be efficacious, this would provide a viable solution for those people who want to decrease their use of drugs that contain undesired ingredients. Other benefits include detailed surveillance of symptoms and documentation of activities, routine medications and supplements that may provide participant and their regular physician or other healthcare provider with useful information for diagnosis and treatment of symptoms should they occur.

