7.1. Study Outcomes Measures

Analysis populations:

The *intent to treat* (ITT) population consists of all participants who are consented, report the onset of indigestion and heartburn, and have taken the study medication at least once. The primary analysis will be in the ITT population.

Primary Endpoint:

The primary endpoint has two components, reduction in indigestion severity and reduction in heartburn severity. Participants will be asked to rate each symptom (bloating, early fullness during a meal, pain or discomfort in the upper abdomen, burning in the upper abdomen, pain/burning in the center of your chest, nausea, vomiting, burping) on a 4-point Likert scale at 4 time points: prior to taking the test product, 15, 30, and 60 minutes after taking the test product. The improvement in symptoms from baseline will be evaluated on a pairwise basis separately for each component and each time point. P-values will be computed for the improvement.

There is no control group for the primary analysis.

Secondary Endpoints:

Secondary endpoints will be gathered on the subjective experience of these participants related to general health, personal experience with the test product. The secondary endpoints will be self-reported by the participant on their online portal. There will be a questionnaire related to general health and the subjective experience of the participant administered at baseline and at study exit.

The purpose of the secondary analyses is to investigate the association between various baseline and other measurements and outcomes. These secondary analyses are considered hypothesis generating, and the descriptions are somewhat informal. The trial data may suggest secondary analyses not described here.

Secondary endpoints:

- The time to other intervention will be analyzed.
- A longitudinal analysis will be performed for participants who report on more than one incident of heartburn or indigestion.
- Adverse events will be summarized.
- An additional data presentation will consist of results from both Treatment and Control
 in similar studies appearing in the literature. There will be no formal statistical
 comparison of results from this study and historical studies.
- The Net Promoter Score will be summarized and compared against outcomes.
- Comparison against normal behavior will use the paired sample t-test.

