13.1.4. Appendix D Baseline Form

Baseline

 Demograph 	ics
-------------------------------	-----

- a. Race/Ethnicity (Black or African American, White, Asian, American Indian or Alaska Native, Native Hawaiian or another pacific islander, other: _____, do not want to share)
- b. Sex (M, F, or Do not want to share)
- 2. On average how often do you get Indigestion and Heartburn? (few times a year, once a month, A few times a month, once a week, 2-3 times a week, Everyday)
- 3. How long does it usually take for your symptoms to reach maximum intensity? (0-30 min, 31 min- 1 hour, +1 hour)
- 4. How long do your symptoms usually last without medication? (0-30 min, 31 min- 1 hour,, 1-2 hour, >2 hours, do not resolve)
- 5. How long do your symptoms usually last with medication? (0-30 min, 31 min- 1 hour,, 1- 2 hour, >2 hours, Do not resolve)
- 6. On average how bad are your symptoms without medication? (1-10)
- 7. On average how bad are your symptoms with medication? (1-10)
- 8. What symptoms do you experience when you are having an episode of Heartburn/Indigestion? (Check all that apply)
 - a. bloating
 - b. early fullness during a meal
 - c. pain or discomfort in the upper abdomen
 - d. burning in the upper abdomen
 - e. pain/burning in the center of your chest
 - f. nausea
 - g. vomiting
 - h. burping
 - i. other:
 - j. None of the above
- Do any of the following bring on or trigger your symptoms of indigestion or heartburn? (Check All That Apply)
 - a. Overeating
 - b. Eating too quickly
 - c. Fatty/greasy foods
 - d. Spicy foods
 - e. Caffeine
 - f. Alcohol
 - g. Smoking
 - h. Other:
 - i. None of the above

- 10. Do you take medications to treat your symptoms? (yes/no)
 - a. What medication do you take? (free response)
 - b. how long do you wait before taking medication?
 - i. Right away
 - ii. Within an hour
 - iii. 1-2 hours
 - iv. >2 hours

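### Supplements are permitted after one hour but only medication is to be recorded, so time to other intervention may show fewer or later interventions than occurred

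*Combined protocol and SAP*

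**What the plan says.** Section 4.2 bars other medication or supplementation for symptom relief, with CBD products named, during the hour after the test product. It then lifts the bar once the one-hour report has been made: the "participant may take other medications or supplements. If medication is taken, the participant will record this in their symptom diary". The second sentence of that quote, on recording, is narrower than the first, on what is permitted. Section 4 has the same recording sentence. Section 6.1 introduces its recording instruction with "If the participant takes any other medication outside of the test product", and directly beneath it allows alternative medications or supplements after one hour.

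The forms follow the narrower wording. Appendix E asks "Did you need to take another" medication, gives three lines headed Medication with dose and time, and then asks about resolution after the alternative medication. Appendix F item 6 asks whether the product prevented use of alternative medication.

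Section 7.1 lists the endpoint: "The time to other intervention will be analyzed". Neither it nor any other section defines an intervention. Section 7.3 assigns Kaplan-Meier to time-to-event variables and leaves further detail to an SAP to be written later.

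At baseline, the Section 6.2 schedule has a row for medications and supplements, marked before receipt of the product. The Appendix D item on usual treatment begins "Do you take medications to treat your symptoms? (yes/no" and does not mention supplements.

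**The concern.** The endpoint is worded as time to other intervention, and the protocol permits two kinds of intervention after the first hour. It asks participants to record one of them. The diary's own reminder names medications and supplements as separate things, so a participant who has just read it may reasonably answer No to the medication question after taking a supplement.

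What is at stake is a descriptive curve. An intervention that is not written down becomes either no event or a later one, and both make the product look better. There is a smaller side effect. A supplement taken after one hour and not recorded could lead later resolution of symptoms to be credited to the test product in the diary's resolution question. The SAP can define the endpoint, but it cannot recover use that was never collected.

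**Working it through.** **Step 1: set the text side by side.**

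| Place | What may be taken | What is to be recorded |
|---|---|---|
| Section 4 | Alternative medication, after one hour | Medication |
| Section 4.2 | Medications or supplements, after the one-hour report | Medication |
| Section 6.1 | Medications or supplements, after one hour | Any other medication |
| Section 6.2 schedule | – | Medications and supplements, once, before receipt; not at Events 1 to 3 or at exit |
| Appendix E | Reminder excludes medications and supplements in the first hour | Another medication; three Medication lines; resolution after alternative medication |
| Appendix F item 6 | – | Alternative medication |

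No field during an episode or at exit asks for supplements by name.

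**Step 2: trace the effect on the endpoint.** Suppose a supplement counts as an intervention.
- Unrecorded supplement, no medication: no event is counted.
- Unrecorded supplement, then a recorded medication: the event is counted, but late.
- Recorded medication, then an unrecorded supplement: the event is counted at the right time.

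No case produces an extra or earlier event, so any error runs one way.

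**Step 3: illustrate the size.** The plan gives no figure for this endpoint, so there is none to reproduce. The 97 treated participants of Section 7.2 serve below only as a denominator. (That number does reproduce: a paired t-test with mean 0.5, SD 1.5 and two-sided 5%, the level being assumed, gives power 0.9015 at n = 97.)

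Let p be the true share of treated participants who use any other intervention, and s the share of those who take only an unrecorded supplement. Both are assumed.

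Recorded intervention-free share = 1 − p(1 − s)

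| p | True share free | Recorded, s = 0.10 | Recorded, s = 0.50 |
|---|---|---|---|
| 0.20 | 80% | 1 − 0.20 × 0.90 = 82% | 1 − 0.20 × 0.50 = 90% |
| 0.30 | 70% | 1 − 0.30 × 0.90 = 73% | 1 − 0.30 × 0.50 = 85% |
| 0.50 | 50% | 1 − 0.50 × 0.90 = 55% | 1 − 0.50 × 0.50 = 75% |

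At p = 0.30 with 97 treated, true events are 97 × 0.30 = 29.1. Recorded events are 29.1 × 0.90 = 26.2 down to 29.1 × 0.50 = 14.55, that is, about 26 to 15.

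For the time scale, take a constant hazard with a fraction s of events unrecorded, and let those participants remain just as likely to take a recorded medication later. The recorded hazard is then (1 − s) times the true one, and the median is 1/(1 − s) times too long: 1.11, 1.33 and 2.0 for s = 0.10, 0.25 and 0.50. If participants comply, the ratio applies to time after the one-hour mark, because no other intervention is permitted before it.

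**Step 4: check the primary endpoint.** The last primary rating is at 60 minutes, and other products are permitted only after that report. The primary ratings are therefore unaffected if participants comply.

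**The case against.** The best counter-argument is that the protocol does not use medication to exclude herbal products. Section 7.1 calls the plant-based test product the study medication, and the recording instruction in Section 6.1 treats it as one medication among others. In Section 6.1 the permission for supplements sits beneath the recording instruction and can be read as within its scope. The diary lines are open fields, and nothing stops a participant from entering a supplement. This stands to the extent that supplements may be missed. A reader might infer that they will be missed, and the documents do not establish that. It does not remove the point, because Section 4.2 and the diary reminder name the two separately.

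Some further inferences are tempting but not supported:
- **That supplements are the likely second step.** Section 2.2.2 does say "these consumers are seeking natural, plant-based alternatives for symptom relief", but it describes consumers in general. Section 5.1 defines the target population only by occasional symptoms, and Section 2.1 names antacids as the most common treatment. Supplement use is plausible; its frequency is unknown.
- **That home remedies are also lost.** The documents never mention them. Whether they should count is a choice of endpoint definition.
- **That the baseline record has the same gap.** The schedule plans to collect supplements before receipt of the product. The defect there is that Appendix D does not carry out that row; item 10a is at least free text.
- **That every unrecorded supplement counts as an episode without intervention.** A recorded medication in the same episode still counts as an event.

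**Conclusion.** The mismatch is in the current text, and nothing elsewhere closes it. Following the recording instructions as written can lose or delay events for time to other intervention, in one direction only. The size is not estimable from the documents. The figures above rest on assumed rates; the proportions also assume that these supplement users take no recorded medication. The direction assumes that a supplement counts as an intervention, which the protocol leaves undefined.

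A reader might take this as bias in the trial's efficacy result. The documents do not support that. The endpoint is secondary, Section 7.1 calls the secondary analyses hypothesis generating, and there is no control arm, so the effect is a more flattering descriptive curve and not a distorted comparison. The sample size is not affected. The point is an inexpensive improvement to data capture, best made before data collection because the loss cannot be repaired afterwards.

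**What to change.** 1. In Sections 4, 4.2 and 6.1, extend the recording sentence to *any other medication or supplement (including CBD products)*.
2. In Appendix E, reword the question on further treatment, the three product lines and the follow-up resolution item to match, collecting product, amount and time.
3. Reword Appendix F item 6 in the same terms.
4. Define the event for time to other intervention as the first such medication or supplement taken for the episode.
5. Separately, add supplements to Appendix D item 10, so that the form collects what the Section 6.2 schedule marks before receipt of the product.

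These changes concern recording and definition only; what participants may take, and when, is left as it is. The cost is three protocol sentences, a few form items and one definition. The observed rate of other intervention may look less favourable as a result.
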